## Prevalence of Polycystic Ovary Syndrome in Trinidad

## **Abstract**

According to World Health Organization (WHO), in 2010, Polycystic Ovarian Syndrome (PCOS) affected approximately 116 million women worldwide (3.4% of the population). It has been considered one of the most common causes of female infertility and the most common endocrine disorder. The standard diagnosis for the syndrome dates back to international conferences organized by the National Institutes of Health (NIH) in 1990 and the Rotterdam European Society of Human Reproduction and Embryology/ American Society for Reproductive Medicine (ESHRE/ASRM) sponsored PCOS consensus workshop group in 2003 and 2004. Clinical manifestations of the disease may include menstrual irregularities, amenorrhea, ovulation-related infertility, polycystic ovaries, and signs of androgen excess such as acne and hirsutism. This condition may also lead to chronic diseases such as obesity, type 2 diabetes (T2D), dyslipidaemia, and cardiovascular events. Despite the increasing knowledge concerning PCOS, the global picture of the disorder is deficient in a number of geographic regions. Understanding the global prevalence will help to better assess the public health and economic implications of PCOS in Trinidad, allow for improved screening methods, help elucidate the underlying factors and foster improved understanding of the molecular mechanisms in improving the evolutionary process.

## **Aims and Objectives**

### Statement of Problem

Despite the increasing knowledge concerning PCOS, the global picture of the disorder is deficient in a number of geographic regions. Understanding the global prevalence and phenotypic presentation of any common disorder, including PCOS, allows for:

1. A determination of the prevalence and associated morbidities of the disorder, to better assess the public health and economic implications of PCOS in this region.
2. A determination of the phenotype of PCOS in this region, allowing for improved screening methods.
3. The elucidation of underlying environmental or ethnic factors that may affect the prevalence, severity or complications of the disorder, via comparison of data between countries.
4. The elucidation of genetic variants underlying the disorder in this region, fostering and improved understanding of the molecular mechanisms underlying the disorder and a better understanding of the evolutionary selection processes that have paradoxically resulted in the current high prevalence of the disorder in the face of obvious reproductive deficits.

### Benefit

These data would not only lead to improved understanding of the public health implications of the disorder in Trinidad, but also potentially highlighting novel etiologic avenues and therapeutic targets.

### Aims and objectives

#### Primary:

1. To determine the prevalence of PCOS among women of reproductive age (a selected population (18 to 45)) in Trinidad.

#### Secondary

2. To determine the distribution of phenotypes among women diagnosed with PCOS in the above objective overall and by ethnicity. PCOS sub phenotypes are as follows: Phenotype A – clinical and/or biochemical hyperandrogenism (HA) and oligi-/anovulation (OA), and polycystic ovarian morphology (PCOM); B – HA and OA; C – HA and PCOM; and D – OA and PCOM;
3. To determine the risks for, metabolic syndrome, depression, obstructive sleep apnea symptoms, fibroids, and general health issues for PCOS women versus women without PCOS in the age groups 18 – 45 years.
4. To determine the genotype of PCOS in Trinidad.

#### Outcome measures and variables

## Outcome measures (dependent variables)

- a) Primary outcome
  - i) Prevalence of PCOS and its symptoms
- b) Secondary outcome
  - i) Phenotype of PCOS
  - ii) Genotype of PCOS
  - iii) Prevalence and prevalence ratio for PCOS subphenotypes in Trinidad, odds ratio for metabolic syndrome, depression, obstructive sleep apnea symptoms, fibroids, and general patient health issues, adjusted for age, ethnicity, BMI, treatment (OCP), and socioeconomic parameters.

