#### Strategies for Sampling, Recruitment and Retention

Participants will be sampled proportionally from all 8 zones as shown above in Trinidad. Approximately 124 women in the reproductive age (18 – 45 years old) will be randomly sampled from each zone. Houses will be numbered and random numbers of these houses will be generated using random number calculator. In each sampled house, females would be prescreened and those that satisfy our inclusion criteria would be selected. Telephone numbers of participants will be obtained and follow-up calls made.

Sample size calculations were based on the following formula (32):

$$n = [(Z_{1-\alpha})^2(P(1 - P)/D^2)]$$

where n = individual sample size,  $Z_{1-\alpha} = 1.96$  (when  $\alpha = 0.05$ ), P = assumed prevalence, and D = absolute error.

Sampling units are defined as individual unselected women between the ages of 18 and 45 years, identified in the community. We target power analysis on women who do not use hormonal contraception. We assume a conservative response rate of 50% of sampled women. This response rate includes the following parameters:

use of hormone/contraceptive use (15%), excluded due to hysterectomy or ovariectomy (3%), excluded due to pregnancy (2%), refusal to participate (20%), and study drop-out/lost to follow-up (10%).

A conservative prevalence estimate for PCOS based on a review of nine studies conducted in the general population using the Rotterdam 2003 definition is 13.4% (4, 5, 33-39). Using the above formula, a sample size of 495 individuals will be required to determine the prevalence with an absolute error of  $\pm 3\%$ . Assuming a 50% enrollment rate, 990 women would need to be approached for study inclusion.

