All blood samples will be stored and transported to the laboratory in cooler boxes containing ice packs immediately after collection. At the laboratory, the sample will be separated into serum, plasma and whole blood by centrifugation for 20 minutes at 3000 rpm. The biological specimens will be stored, in small aliquots (of 0.5 ml), in 1.5 to 2.0 ml plastic containers (about 12 cryovials) able to withstand temperatures of -80°C.

Samples for hormonal assay and initial evaluation will be batched at regular interval for analysis to provide study participants with timely results, allow classification of participants, and minimize the impact of inter-assay variability. At the end of the study, a repeat analysis of biological samples for androgen levels and insulin estimation will be performed at a reference laboratory. Each subject will also complete the following standardized data instruments or forms as appropriate: FG Score self-assessment, SF-12, Beck depression inventory, Epworth sleepiness scale, and uterine fibroid assessment (see attached).

We propose to establish collaboration between the University of Lagos and the Laboratory of [name], a world renowned scholar on the subject of PCOS in the United States. The genetic analysis will be performed at the Laboratory at the Department of Pre-clinical Sciences. The initial evaluation and classification of study participants will be done using the flow chart/diagnostic tree by Azzizz et al. (Figure 1).

Related or mimicking disorders will be excluded using history, physical examination, and serum TSH, prolactin and 17-OH progesterone. Participants with hypothyroidism on thyroxine replacement therapy will not be recruited for the study until TSH level is normal. Study participants with elevated 17-OH progesterone > 2ng/dl (or 200 ng/dl) will have non-classical congenital adrenal hyperplasia (NCAH).

A summary of initial and follow-up procedures.

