**Data management and Statistical analysis:**

Data entry, data processing, and statistical analysis will be done using IBM Statistical

Software for Social Sciences (SPSS, Inc., Chicago, IL) version 20.0. Continuous variables (such as age, anthropometric measurements, laboratory values of assay) will be checked for normality using one-sample

Kolmogorov-Smirnoff test, and expressed as means  $\pm$  standard deviation or median  $\pm$  interquartile range (for data that are not normally distributed).

Categorical variables (such as race, socioeconomic characteristics) will be expressed as frequencies with accompanying percentages. Differences between groups will be compared using the Pearson's Chi-square test or Fisher's exact test for categorical variables. Odds ratio and the corresponding 95% confidence intervals (CI) will be presented. The student t test and ANOVA will be used to compare difference between groups for normally distributed continuous variables. Comparison of continuous variables that were not normally distributed will be done using non-parametric (Mann-Whitney U test or Kruskal-Wallis test) inferential statistical test.

Linear and logistic regression analysis (univariate and multivariate) will be performed to evaluate the relationship between dependent and independent variables. Test of statistical significance will be set at p-value less than 0.05.

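### Depression, sleepiness and general health are measured as scores, but the plan names only an adjusted odds ratio for them and shows no cut-point; an adjusted score difference should be reported as well.

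*Combined protocol and SAP*

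**What the plan says.** The third secondary outcome, under the outcome measures heading, is an "odds ratio for metabolic syndrome, depression, obstructive sleep apnea symptoms, fibroids, and general patient health issues". The same item then sets out the covariates of that odds ratio: "adjusted for age, ethnicity, BMI, treatment (OCP), and socioeconomic parameters". The list appears twice in the protocol with the same content. It serves the third objective: "To determine the risks for, metabolic syndrome, depression, obstructive sleep apnea symptoms, fibroids, and general health issues for PCOS women versus women without PCOS".

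The study procedure section has each participant complete the "FG Score self-assessment, SF-12, Beck depression inventory, Epworth sleepiness scale, and uterine fibroid assessment", and the data collection section repeats this. The forms are described as attached and are not part of the text available here. No scoring rule, cut-point or definition of a case appears in the visible text for the Beck inventory, the Epworth scale or the SF-12.

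The statistical analysis section plans t tests or ANOVA for normal continuous variables, rank tests for non-normal ones, and both linear and logistic regression. It matches none of these to a named outcome. On testing it says: "Test of statistical significance will be set at p-value less than 0.05".

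The only sample size calculation is for the precision of the prevalence estimate. No power or detectable difference is stated for PCOS versus non-PCOS comparisons.

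**The concern.** An odds ratio needs either a binary event or an ordinal model. The plan names no ordinal model, so its wording points towards splitting each score in two. The visible text does not say where.

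Two things are at stake:

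- **Information.** A split score treats all women on the same side of the cut as equal. The PCOS group is likely to be the small one, so its comparisons have little precision to give away.
- **Freedom of choice.** With three instruments, no cut-point on view and a 0.05 threshold, the definition of an event could be settled after the data are seen. For general health as measured by the SF-12, the text does not say what the event would be.

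A covariate-adjusted analysis of the full score avoids both problems. The regression method it needs is already listed, but it is not assigned to these outcomes.

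**Working it through.** **Inputs from the protocol.** The sampling section gives an assumed prevalence "using the Rotterdam 2003 definition is 13.4" percent, an absolute error of 3 percentage points and z = 1.96. It then says: "Using the above formula, a sample size of 495 individuals will be required to determine the prevalence with an absolute error of" 3 points, and "Assuming a 50% enrollment rate, 990 women would need to be approached for study inclusion". Alpha is 0.05, taken as two-sided to match z = 1.96.

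**Inputs assumed, not in the documents.** Scores are normal with SD 1, there is no covariate adjustment, and the effect size and cut position are as shown below.

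**Step 1: the plan's own figure.** n = 1.96² × 0.134 × 0.866 / 0.03² = 495.3, which reproduces 495. Then 495 / 0.50 = 990.

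**Step 2: group sizes.** 0.134 × 495 = 66.3, so about 66 cases and 429 non-cases. At prevalences of 10.4% to 16.4% (13.4% ± 3 points) the case count is about 51 to 81.

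**Step 3: full score.** The SE of a mean difference, in SD units, is √(1/66 + 1/429) = 0.1322. The difference with 80% power is (1.96 + 0.842) × 0.1322 = 0.370.

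**Step 4: the same difference after a cut.** Let p0 be the share of non-cases above the cut. The share of cases above it is p1 = 1 − Φ(Φ⁻¹(1 − p0) − 0.370). Power is Φ[(p1 − p0 − 1.96 × SE0) / SE1], where SE0 uses the pooled proportion and SE1 the separate ones.

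Worked for p0 = 0.20:
- p1 = 1 − Φ(0.842 − 0.370) = 0.3187
- pooled proportion = (429 × 0.20 + 66 × 0.3187) / 495 = 0.2158
- SE0 = √(0.2158 × 0.7842) × 0.1322 = 0.0544
- SE1 = √(0.20 × 0.80/429 + 0.3187 × 0.6813/66) = 0.0605
- power = Φ[(0.1187 − 0.1066) / 0.0605] = Φ(0.20) = 58%

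| Non-cases positive | Cases positive | Power after cut | Loss from 80% |
|---|---|---|---|
| 50% | 64.4% | 59% | 21 points |
| 30% | 43.9% | 61% | 19 points |
| 20% | 31.9% | 58% | 22 points |
| 10% | 18.1% | 50% | 30 points |

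A simulation (4000 runs per setting) gave 80–81% for the t test and 61%, 61%, 58% and 49% for the chi-square test at the same four cuts.

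**Step 5: how far the loss depends on effect size.** With 66 versus 429 and cuts leaving 50% to 10% of non-cases positive:

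| True difference (SD) | Loss in power (points) |
|---|---|
| 0.2 (full-score power only 33%) | 10 to 14 |
| 0.3 | 18 to 26 |
| 0.4 | 18 to 30 |
| 0.5 | 11 to 22 |
| 0.6 | 4 to 12 |
| 0.8 | 0.2 to 1.5 |

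**Step 6: skewed scores.** In a simulation with exponential scores (scale ratio 1.42), the t test had 78–79% power and the Mann-Whitney test 61–62%. The cut score had 41%, 55%, 60% and 62% at 50%, 30%, 20% and 10% positive. Against Mann-Whitney, the plan's test for non-normal data, the loss runs from about 20 points to about 0. Against the comparison of means it stays at about 16 points or more (78 − 62).

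**Step 7: more cases.** If 30% of the 495 were cases (148 versus 347, an illustrative figure), a 0.37 SD difference has 96% power on the full score. After a cut, power is 85%, 84%, 80% and 69% at the same four positions.

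**The case against.** **The plan does not force a cut.** The statistical section already allows tests and linear regression on continuous variables, and an ordinal model would yield an odds ratio from the whole score. This stands. A reader might infer from the outcome list that the scores must be split in two, but the documents do not go that far. They name an odds ratio and leave outcomes unmatched to methods.

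**A cut-point may exist on the attached forms.** This also stands. One can say only that none appears in the visible text, not that one will be picked after the data are in.

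**The odds ratio suits the objective.** The third objective asks about risks. In a prevalence study, whether more women with PCOS screen positive is a fair public health question, and a difference in mean score answers a different one. This is a good reason to keep the odds ratio and not to demote it.

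**The power loss is conditional.** The 0.37 SD was solved for, not taken from the protocol, and it lies near where the loss is largest. The figures are also unadjusted, whereas the planned odds ratio is adjusted. Both points stand, so no single loss can be quoted as a fact about this study.

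**There may be more than 66 cases.** The inclusion criteria require at least one PCOS-type feature, which would raise the case fraction above the general-population 13.4%. Oral contraceptive use is an adjustment covariate, although the 495 counts untreated women. If the 15% hormonal users stayed in, cases would be about (0.50 + 0.15) × 990 × 0.134 = 86. This stands as a caution on the count. More cases make smaller effects detectable, but they do not remove the cost of cutting. At whatever effect gives 80% power on the full score, power after a cut stays at about 42% to 62% for case counts from 51 to 200.

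**Conclusion.** The point holds as a gap in specification with a cheap and usually more powerful remedy. An adjusted odds ratio is the only outcome-specific effect measure for three domains measured by scores. No cut-point or event definition is visible, and linear regression is listed without being assigned to them.

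If the scores are dichotomised, an effect detectable with 80% power on the full score (0.37 SD, 66 versus 429) keeps about 50% to 61%. This rests on normal scores, no covariate adjustment, 13.4% prevalence among 495 women, and 10% to 50% of non-cases above the cut. Over the effect sizes and score shapes examined, the loss for such cuts runs from about 0 to about 30 points, taking Mann-Whitney as the comparator for skewed scores.

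A reader might infer that a loss of 20 to 30 points is certain, or that the study cannot answer its third objective. The documents support neither: they fix no effect size, score distribution or cut, and the case count could exceed 66. The primary prevalence outcome is unaffected, and metabolic syndrome and fibroids are not part of this point.

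**What to change.** In both copies of the secondary outcome list and in the statistical analysis section:

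1. For the Beck inventory, the Epworth scale and the SF-12, add the covariate-adjusted PCOS versus non-PCOS difference in score with its 95% CI. Use linear regression with robust standard errors and the covariates already listed, and report it alongside the odds ratio.
2. Keep the odds ratio, which answers the risk wording of the third objective, only where a published cut-point for that instrument is written into the SAP before analysis.
3. Where no cut-point is specified, for example for the SF-12, report the score difference alone.

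No new data are needed and linear regression is already in the plan, so the change is to SAP wording. The cost is one extra analysis per instrument and a second effect measure that may not always agree with the first.

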## Background

According to World Health Organization (WHO), in 2010, Polycystic Ovarian Syndrome (PCOS) affected approximately 116 million women worldwide (3.4% of the population). This condition caused symptoms in about 5-10% of women of reproductive age (12 – 45 years). It has been considered one of the most common causes of female infertility and the most common endocrine disorder (Boomsma, Fauser, and Macklon 2008; Teede, Deeks, and Moran 2010). The standard diagnosis for the syndrome dates back to international conferences organized by the National Institutes of Health (NIH) in 1990 (Zawadzki and Dunaif 1992) and the Rotterdam European Society of Human Reproduction and Embryology/ American Society for Reproductive Medicine (ESHRE/ASRM) sponsored PCOS consensus workshop group in 2003 and 2004 (Rotterdam ESHRE/ASRM-sponsored PCOS consensus workshop group 2004). Clinical manifestations of the disease may include menstrual irregularities, amenorrhea, ovulation-related infertility, polycystic ovaries, and signs of androgen excess such as acne and hirsutism. This condition may also lead to chronic diseases such as obesity, type 2 diabetes (T2D), dyslipidaemia, and cardiovascular events (Palomba et al. 2015; Mohammed and Nayak 2017).

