***Study specific medical examination will include:***

- Waist and hip circumferences measurement
- Hirsutism assessment
- Acne assessment
- Alopecia assessment
- Acanthosis nigricans assessment

Data Collection:

Types of data:

Independent variables

1. Socio-demographic variables
2. Baseline characteristics

Dependent variables

3. Primary outcome
  - I. Prevalence of PCOS
4. Secondary outcome
  - II. Phenotype of PCOS
  - III. Genotype of PCOS
  - IV. Prevalence of obesity
  - V. Prevalence of hirsutism
  - VI. Prevalence of diabetes

Data collection instrument:

The methods of collecting data for assessment of study objectives include the use of standardized interview-based medical forms; surveys; physical examination.

The CRF developed for this study include; clinical and anthropometric section; radiological report section and laboratory result section. The questionnaire section will seek information on socio-demographic variables, reproductive history with emphasis on menstrual cycle (dating and regularity) and gynecological history, hirsutism, acne, medications, and family history. The anthropometry and clinical section will document the physical findings such as hirsutism, acne, alopecia, acanthosis nigricans, and thyroid enlargement. The pelvic ultrasonographic findings will be recorded in the laboratory result section. Subjects will also complete the

following standardized data instruments or forms as appropriate: FG Score self-assessment, SF-12, Beck depression inventory, Epworth sleepiness scale, and uterine fibroid assessment.

Expected duration of subject participation is approximately from 1 to 3 cycles or 12 weeks. Approximate time to complete enrollment is 9 to 12 months. Approximate time to complete study is 18 to 24 months.

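### The only covariate-adjusted odds ratios specified for objective 3 condition on BMI, although the protocol says PCOS may lead to obesity; an adjusted model without BMI should be pre-specified beside them

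*Combined protocol and SAP*

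**What the plan says.** Objective 3 (Aims and objectives, Secondary) covers several conditions and ends with "general health issues for PCOS women versus women without PCOS in the age groups 18 – 45 years". It does not say that the comparison should be independent of BMI.

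The secondary outcomes (Outcome measures and variables, stated once after the aims and again after the Background) give the odds ratios for these conditions as "adjusted for age, ethnicity, BMI, treatment (OCP), and socioeconomic parameters". The same set appears in both places, and no other adjustment set appears anywhere.

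On the place of BMI, the Background says: "This condition may also lead to chronic diseases such as obesity, type 2 diabetes (T2D), dyslipidaemia, and cardiovascular events". The Abstract says the same. The Data Collection list includes "Prevalence of obesity" among the dependent variables.

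The section Data management and Statistical analysis adds: "Odds ratio and the corresponding 95% confidence intervals (CI) will be presented", next to the chi-square and Fisher tests, and "Linear and logistic regression analysis (univariate and multivariate) will be performed to evaluate the relationship between dependent and independent variables". It names no covariates, no adjusted model without BMI and no mediation analysis.

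**The concern.** Objective 3 is worded as a plain contrast between two groups of women. The protocol's stated purpose includes measuring the morbidity that accompanies PCOS in order to judge its public health and economic weight. If part of that morbidity arises because PCOS raises weight, a model that holds BMI fixed leaves that part out. The plan treats weight both as something PCOS may produce and as something to hold constant, and does not say which reading of objective 3 the adjusted odds ratio is meant to serve.

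A reader who wants the contrast adjusted for age, ethnicity and socioeconomic factors, with weight left free, will find no such estimate. If the covariate set is reconsidered only after the data are seen, the choice is open to the charge of having been made on the results.

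**Working it through.** **The plan's own figure.** There is none on this point. The only sample-size figure (495) concerns the precision of the prevalence estimate and does not bear on the choice of covariates.

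**Step 1. What each planned or missing estimate would contain.**

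| Estimate | In the plan? | Age, ethnicity, socioeconomic factors | BMI |
|---|---|---|---|
| Odds ratio beside the chi-square/Fisher test; univariate logistic regression | Yes | Not adjusted | Not adjusted |
| Adjusted odds ratio in the outcome list | Yes | Adjusted | Adjusted |
| Adjusted odds ratio without BMI | No | Adjusted | Not adjusted |

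The third row is the gap. The first row cannot stand in for it, because it is open to confounding by factors that the plan itself adjusts for.

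**Step 2. Direction and possible size.** The documents give no inputs, so every figure here is an assumption. Obesity (yes/no) stands in for BMI, and there are no other confounders.

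- Outcome risk in non-obese women without PCOS: 15%, so odds 0.15/0.85 = 0.1765
- Obesity prevalence without PCOS: 25%; with PCOS: 25%, 35%, 45% or 55%
- Odds ratio of obesity for the outcome: 2 or 4
- Odds ratio of PCOS given obesity status (the analogue of the BMI-adjusted estimate): 1.5, then 1.0 and 2.0

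Formulas: group risk = p × (risk if obese) + (1 − p) × (risk if not obese), where p is the obesity prevalence in the group. The odds ratio without conditioning is the ratio of the two groups' odds. The share of the log odds ratio removed is 1 − ln(conditional OR)/ln(unconditional OR).

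Worked case, with obesity 25% against 45%, obesity odds ratio 4 and conditional odds ratio 1.5:

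- Without PCOS: obese odds 0.1765 × 4 = 0.7059, risk 0.4138. Group risk = 0.25 × 0.4138 + 0.75 × 0.15 = 0.2159, odds 0.2754.
- With PCOS: non-obese odds 0.1765 × 1.5 = 0.2647, risk 0.2093. Obese odds 0.7059 × 1.5 = 1.0588, risk 0.5143. Group risk = 0.45 × 0.5143 + 0.55 × 0.2093 = 0.3465, odds 0.5303.
- Odds ratio = 0.5303/0.2754 = 1.93. Share removed = 1 − ln 1.5/ln 1.93 = 0.38.

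All cases with conditional odds ratio 1.5 (range: obesity odds ratio 2 to 4):

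| Obesity in PCOS | OR without conditioning | Share of log OR removed |
|---|---|---|
| 25% (no difference) | 1.49 to 1.45 | none (−2% to −9%) |
| 35% | 1.60 to 1.68 | 14% to 22% |
| 45% | 1.72 to 1.93 | 25% to 38% |
| 55% | 1.84 to 2.20 | 34% to 49% |

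Across the three rows with more obesity in PCOS, a conditional odds ratio of 2.0 gives a share of 8% to 34%. A conditional odds ratio of 1.0 gives 1.08 to 1.52 without conditioning, so the whole association disappears on conditioning. The first row shows the non-collapsibility of the odds ratio alone: it is small and works the other way, so it does not account for the gap in the other rows.

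**Step 3. What the arithmetic cannot show.** The calculation uses only how common obesity is in each group and the outcome risk by obesity and PCOS status. It does not use the direction between PCOS and obesity. If obesity came first and raised the chance of PCOS, the same data would give the same pair, 1.50 and 1.93, and then 1.93 would be the confounded figure. One set of cross-sectional data is compatible with either reading.

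**The case against.** **Odds ratios without BMI are already planned.** This stands in part. A reader might infer that the plan offers nothing except BMI-conditional estimates. The statistical section does not support that, since it plans odds ratios with confidence intervals and univariate regression. What is missing is narrower: an estimate adjusted for the other factors but not for BMI.

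**BMI may belong in the model.** This stands. The protocol's causal wording is hedged, and by its title one entry in the reference list concerns obesity as an influence on the risk of PCOS. If BMI partly precedes PCOS, leaving it out leaves confounding in. A reader might infer that adjusting for BMI is an error, or that the model without BMI is the true answer to objective 3. Neither follows, because the objective does not settle which contrast is meant.

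**The harm can be overstated.** This also stands. A reader might infer that the plan would report no excess risk and so reverse its public health message. Obesity and diabetes prevalence are separate outcomes, anthropometric measurements are among the continuous variables to be analysed, and crude odds ratios are planned, so weight differences would not be hidden.

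**Scope.** The argument is clearest for metabolic syndrome. The documents describe no route through weight to depression, fibroids or general health. Nor would a second model give a general-population contrast, because inclusion criterion (b) requires every participant to have at least one hyperandrogenic or ovulatory feature. That is a separate matter.

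**Conclusion.** The concern holds as a gap in specification. The only covariate-adjusted odds ratios for objective 3 hold BMI fixed, while the protocol says PCOS may lead to obesity and lists obesity as an outcome. If PCOS does raise BMI, those odds ratios omit the part of the association that passes through weight, and the planned crude odds ratios do not supply it in adjusted form.

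The size cannot be determined from the documents. The figures above rest on an assumed baseline risk, assumed obesity prevalences, assumed odds ratios and no other confounding. To read the gap as a mediated effect also requires that obesity follows PCOS. A reader might take 1.60 to 2.20 against 1.5 as a forecast of bias in this study; it is only an illustration. If BMI is similar in the two groups, the two adjusted models will nearly agree. This is a free improvement to a secondary objective and does not affect the primary prevalence estimate.

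**What to change.** In both statements of the secondary outcomes, pre-specify two adjusted models for each objective 3 outcome and report them side by side:

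1. Adjusted for age, ethnicity, treatment (OCP) and socioeconomic parameters.
2. The same covariates plus BMI, labelled as the association not explained by current BMI.

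OCP treatment stays in both models, as in the plan's own set, so that the two differ only in BMI. State that neither model alone separates mediation from confounding by BMI, and repeat the two covariate sets in Data management and Statistical analysis, which at present names none.

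Height and weight are already measured and the other covariates are already in the plan's adjustment set, so no new data are needed. The cost is one extra regression per outcome and a longer table.
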